5.5 Committees

IMPACT-AF will be organized similar to other successful health management / clinical studies. See Appendix 6.1

5.5.1 Executive Committee:

The project Executive Committee is responsible for study oversight. Participation includes:

- [name], [name], [name], [name], [name], [name], [name];
- NS Department of Health and Wellness; and,
- [name], Bayer.

A Project Chairperson from the investigator team will be responsible for overall project supervision and chairing of all committee meetings. Executive Committee members are expected to: actively participate in committee meetings; respect confidentiality of all information discussed; serve for the duration of the project, but may resign by providing the Committee Chair with written notice two months in advance of the effective date of their resignation. Each member has one vote on committee decisions. The quorum for all meetings shall consist of a majority of the voting members in attendance. Committee expenses / honoraria, if applicable, are provided from within the project budget.

- Mandate: Responsible for overall project governance including all operational and budget issues.
 - The Project Office coordinates day-to-day management issues.
- Meets frequently, usually bi-monthly at project start and monthly thereafter (or as required). Meeting minutes will serve as record of Committee activities to be distributed within 15 days following the meeting.
- Reports to the Advisory Committee.
- Administrative support provided by the Project Office.

5.5.2 Advisory Committee:

The project Advisory Committee, a broad-based, multi-stakeholder group reflective of all partners, will be responsible to provide expertise, guide strategic decisions, inform and communicate with their representative organization(s) regarding project development, implementation, evaluation and or knowledge translation. This committee of 15-20 participants is expected to include representatives from:

- NS Department of Health and Wellness/Provincial Programs
- Heart and Stroke Foundation Nova Scotia
- Patient representative
- Doctors Nova Scotia
- Pharmacy (retails chains, independents and or the Association)
- Long Term Care organization(s)
- Bayer Healthcare
- Clinical Advisors (Neurology / Hematology / Geriatrics)
- Canada Health Infoway
- Health IT vendors (TELUS Health)
- Canadian Cardiovascular Society
- Provider representatives (FPN, NP or RN rep)
- NS Health Research Foundation
- One or more District Health Authority representatives
- Other participants may be added e.g. NSCAD.

Advisory Members are expected to: actively participate in committee meetings; respect confidentiality of all information discussed, as appropriate; serve for the duration of the project, but may resign by providing the Committee Chair with written notice two months in advance of the effective date of their resignation. Each member has one vote on committee decisions. The quorum for all meetings shall consist of a majority of the voting members in attendance. Committee expenses / honoraria, if applicable, are provided from within the project budget.

- Mandate: Concerned with project development, providing input, guidance and direction on the project, its goals, implementation and any major policy issues / decisions. Responsible for promoting and driving the project in their organizations and across the province.
- Meetings twice yearly.
- Meeting minutes will serve as record of Committee activities to be distributed within 30 days / months following each meeting.
- Administrative support provided by the Project Office.

5.5.3 Adjudication Committee:

An adjudication committee may be created to provide oversight regarding adjudication of certain study outcomes. Anticipated members include: a clinical cardiologist, an electrophysiologist, a neurologist and a haematologist. The committee will be blinded to

treatment allocation if applicable. Meetings will be held as needed subsequent to the collection of data.

5.5.4 External Review Committee:

An external review committee of 4-5 participants may be created to provide visionary oversight and peer-review on a yearly basis. Consideration will be given to non-Nova Scotia, non-Canadian participants. Representatives are likely to include computer scientists, clinical experts, knowledge translation researchers, health services researchers, and health policy makers or researchers.

5.5.5 Other Committees

Other project collaborators / co-investigators (e.g., subject matter experts) are expected to participate in additional project committees (e.g., Technology Development, Sub-Studies, Economics and Knowledge Translation). Participants may include:

- Health Economist, Behavior / Health Psychologist, Communications / Media (e.g., Dalhousie Faculty of Management), Adult / Health Education, Computer Science – Human Interaction
- Membership: Composed of a core group of individuals with particular subject matter expertise.
 - Members are expected to: actively participate in committee meetings; respect confidentiality of all information discussed, as appropriate; serve for the duration of the project, but may resign by providing the Committee Chair with written notice two months in advance of the effective date of their resignation.
 - Ad hoc members as required.
 - Each member has one vote on committee decisions. The quorum for all meetings shall consist of a majority of the voting members in attendance. Committee expenses / honoraria, if applicable, are provided from within the project budget.
- Mandate: Charged with providing subject matter expertise regarding project-related issues / implications of the study.
- Meets as required to address planning and discuss results of economic evaluations. Meeting minutes will serve as record of Committee activities to be distributed within 15 days following the meeting.
- Administrative support provided by the Project Office.

9.0 APPENDIX

9.1. Project Organogram

IMPACT-AF SAP

NOT FOR REPRODUCTION

NCT 01927367

Optimizing primary care management of atrial fibrillation: The rationale and methods of the Integrated Management Program Advancing Community Treatment of Atrial Fibrillation (IMPACT-AF) study Statistical Analysis Plan, Version 1 January 9, 2019

Background

The burden of Atrial Fibrillation (AF), the most common sustained cardiac rhythm abnormality, is growing markedly such that the lifetime risk of acquiring this condition is now around 1 in 4.^{1,2} AF is linked to increased mortality, substantial morbidity, high patient and health care costs,³ as well as impaired quality of life.⁴ In particular, AF is an important and independent risk factor for stroke, increasing the risk of such events by 5-fold and accounting for approximately 15-20% of all strokes.⁵ Since at least a third of AF patients are asymptomatic,⁶ many cases will be identified in outpatient settings when patients are being assessed for other conditions.

Traditionally, the major therapeutic interventions in AF patient care are directed at modifying or reversing the irregular rhythm and fast heart rate and in providing antithrombotic therapy to prevent strokes.⁷⁻⁹

Recently, multi-disciplinary approaches to AF management, centered on specialty AF clinics, have reported encouraging clinical results, including reductions in wait times for specialist assessment, emergency department (ED) visits, hospitalizations, and even mortality. However, such clinics require expert staff, broad collaboration, and special resources including physical space that entail high costs.

Clinical Decision Support Systems (CDSS) are intelligent systems that digitize and operationalize evidence-based guidelines, clinical pathways and algorithms to provide personalized, timely and evidence-informed functions. While the utility of such heath informatics approaches to health care might seem intuitive, this is not always the case. The diversity in the design, functionality and implementation of CDSS in real-life care settings has precluded making sweeping judgments about their clinical effectiveness, particularly over the longer term. While such technologies offer promise, more robust systems need to be developed and their effectiveness assessed, ideally in randomized trials.

We have developed a CDSS tool that aims to empower improvement in overall AF-related care, not simply with regards to antithrombotic management, but also to support effective rate control and treatment of AF risk factors. The tool has been assessed in a preliminary fashion by a general cardiologist, electrophysiologist and primary care physician, working independently to assess the

utility and dependability of the CDSS using mock clinical cases. While it functioned accurately and with seeming efficacy, there remains the need to determine applicability, ease of use and clinical effectiveness in terms of whether AF patient care and outcomes would improve at the population level with its use.

The primary aim of Integrated Management Program Advancing Community Treatment of Atrial Fibrillation (IMPACT-AF) study is to evaluate whether a CDSS tool, available to primary care physicians, and designed to support both practitioners and patients with evidence-based AF management, can improve clinical and patient-reported outcomes by comparison to usual clinical care. It further seeks to establish whether it will better standardize process of care so as to produce more efficient and cost-effective use of time and scarce health care resources as compared to usual care.

Methods

IMPACT-AF is a prospective, randomized, un-blinded, cluster design clinical trial, conducted in the primary care setting of Nova Scotia, Canada.

At least 200 primary care providers are being recruited and randomized at the level of the practice to control (usual care) or intervention (eligible to access to CDSS) cohorts. Over 1,000 patients of participating providers with confirmed AF will be managed per their provider's respective assignment.

Outcomes

Primary Outcome

The IMPACT-AF primary outcome is composite of any AF-related emergency department visit or unplanned CV hospitalization over 12 months.

Secondary Outcomes

Secondary outcomes include comparing the intervention versus usual care over 12 months on the following:

- 1. Any AF-related emergency department visit
- 2. Unplanned cardiovascular (CV) hospitalization
- 3. Strokes
- 4. Systemic embolism / major bleeding
- 5. Mortality
- 6. Anticoagulant therapy
- 7. Access to specialist consultation

- 8. Echo
- 9. Catheter ablations
- 10. EQ5D
- 11. Health care costs

The definitions of all outcome variables for the primary and secondary analyses are found in Appendix 1.

Analysis Plan

This statistical analysis plan follows the JAMA Guidelines for the Content of Statistical Analysis Plans in Clinical Trials ¹³. A summary of all planned analyses is provided in **Table 1**.

Blinded Analyses

All statistical analyses will first be completed using blinded treatment groups (i.e. treatment X and Y).

Presentation of Data

The trial results will be presented according to the CONSORT guidelines for randomized controlled trials (RCTs) 14 . The baseline demographic characteristics of the patients will be summarized by group, reported as a mean (standard deviation [SD]) or median (first quartile, third quartile) for continuous variables and count (percent) for categorical variables (**Tables 2**). All statistical tests will be 2-tailed with α =0.05.

Primary Outcome Analysis

The primary efficacy analysis will be an analysis to compare rates of the composite of any AF-related emergency department visit or unplanned CV hospitalization between Intervention and Usual care over 12 months, with the outcome being treated as number of events (Tables 3). The analysis will follow the intention-to-treat (ITT) principle. While the unit of randomization is the practice/physician, the unit of analysis will be the patient. We will use Generalized Estimating Equations (GEE) —assuming exchangeable correlation structure for patients within the same practice and adjusting for urban and rural practice types to analyze all outcomes¹⁵. Unlike ordinary regression techniques, GEE allows us to estimate the intra-practice correlation among patients within each practice. For time-to-event analysis this is done using frailty-models. The results will be reported as estimate of the effect—reported as hazard ratio [HR], corresponding 95% confidence interval and associated p-values. All p-values will be reported to three decimal places with those less than 0.001 reported as p<0.001. The criterion for statistical significance will be set a priori at alpha = 0.05. The answers to the five questions in the EQ-5D-5L will be converted to health utilities using the Canadian scoring algorithm¹⁶. Cost effectiveness analysis

will be conducted by calculating the incremental cost per QALY gained by the CDSS arm compared with the usual care arm. Due to skewness of costs and health utility distributions, the non-parametric bootstrapping method will be used to estimate the 95% confidence interval for the incremental cost per QALY gained. All analyses will be performed using SAS version 9.4 (Cary, NC).

Secondary Outcomes Analysis

We will estimate the effect of CDSS (intervention) versus usual care (control) over 12 months on the following: any AF-related emergency department visit; unplanned CV hospitalization; strokes; systemic embolism / major bleeding; mortality; anticoagulant therapy; access to specialist consultation; echo; catheter ablations; EQ5D; health care costs (Table 3). The subgroup analyses will be performed by adding an interaction term of the subgroup variable and the intervention variable in the model. The criterion for statistical significance for subgroup analyses will be set at alpha = 0.05. This will not be adjusted for multiple testing as these analyses are exploratory.

Sensitivity Analyses

There are several methods for analyzing cluster RCTs^{17, 18}. We will conduct sensitivity analyses in two ways. Firstly, we will perform sensitivity analyses using commonly used patient-level methods such as random-intercept model method (Table 4a). Secondly, we will also perform sensitivity analyses with the outcome (composite of any AF-related emergency department visit or unplanned CV hospitalization) being treated as a count assuming a Poisson distribution (Table 2). The results will be reported as incidence rate ratio [IRR], 95% CI and associated p-value. We hypothesize that our results will remain robust to the different sensitivity analyses.

Subgroup Analyses

A subgroup analysis will be conducted to compare the effect of CDSS (intervention) versus usual care (control) on the composite of any AF-related emergency department visit or unplanned CV hospitalization, as well as the of number AF Related ED Visits and CV Hospitalizations individually, by location of practice, patient sex, age, CHADS2, CHADS-VASC, hypertension, diabetes and years of practice of family doctor. We will perform these subgroup analyses by regression methods with appropriate interaction terms. This subgroup analysis will be conducted for all primary and secondary outcomes (Tables 5a, 5b and 5c). Our hypothesis is that the effects of the intervention on outcomes differ by subgroups. A sensitivity analysis will equally be conducted for all the different subgroup analyses with the outcome being treated as a count (Tables 5a, 5b and 5c). All the subgroup results will be presented using forest plots reporting estimates of effect as HR or IRR, 95% CI for each subgroup and a p-value of the interaction test.

Dissemination

Upon trial completion, the primary manuscript with the 12-month follow-up results, whether positive, negative or neutral, will be submitted for a peer-reviewed publication to a top medical journal. The final dataset will be shared through an open access data repository once all analyses are completed.

References

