2.2 Study Outcomes

The **primary study outcome** is a composite of unplanned cardiovascular hospitalization at 12 months and AF-related emergency department visits.

Cardiovascular hospitalization is defined as the following:

Any unplanned hospitalization (admission with an overnight stay in hospital) due to one of the following causes: acute coronary syndrome, presyncope / syncope, transient ischemic attack / stroke, atrial fibrillation, flutter, pulmonary embolism / deep vein thrombosis /systemic embolism, worsening congestive heart failure including pulmonary edema or dyspnea of cardiac origin. [81,107]

The **primary safety outcome** is major bleeding.

Major bleeding is to be defined as fatal and/or symptomatic / intracranial bleeding in a critical area or organ, such as brain, intraspinal, intraocular, retroperitoneal, intra-articular or pericardial, or intramuscular with compartment syndrome and /or overt bleeding causing a fall in hemoglobin level of 20 g/L or more, or leading to transfusion of two or more units of whole blood or red cells. [108]

Secondary outcomes address clinical, process of care, quality of life, and cost effectiveness.

Clinical:

- Individual hospitalization elements as noted above.
- Any bleeding
- All cause mortality
- Appropriateness of oral anticoagulant therapy (based on current CCS guidelines, [23])

Process of Care:

- Access to specialist consultation
- Access to echocardiograms
- Access to catheter ablations for AF and atrial flutter

Health-related quality of life (HRQoL)

- HRQoL measured using the EQ-5D-5L questionnaire

Costs:

- The costs associated with the development, implementation, and maintenance of CDSS
- The costs associated with managing and treating patients with AF

Cost effectiveness

- Incremental cost effectiveness ratio between the interventional arm and the control arm

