1) Primary To compare rates of the composite of any AF-related emergency department visit or unplanned CV hospitalization between Intervention and Usual care over 12 months	composite of any AF-related emergency department visit or unplanned CV hospitalization over 12 months	Intervention better than Usual Care	Generalized Estimating Equations (GEE) or frailty models
2) Secondary To compare I vs UC over 12 months on the following: any AF-related emergency department visit	any AF-related emergency department visit	Intervention better than Usual Care	GEE or frailty models
unplanned CV hospitalization	unplanned CV hospitalization	Intervention better than Usual Care	GEE or frailty models
strokes	strokes	Intervention better than Usual Care	GEE or frailty models
systemic embolism / major bleeding	systemic embolism / major bleeding	Intervention better than Usual Care	GEE or frailty models
mortality	mortality	Intervention better than Usual Care	GEE or frailty models
anticoagulant therapy	anticoagulant therapy	Intervention better than Usual Care	GEE or frailty models
access to specialist consultation	access to specialist consultation	Intervention better than Usual Care	GEE or frailty models
echo	echo	Intervention better than Usual Care	GEE or frailty models

catheter ablations	catheter ablations	Intervention better than	GEE or	frailty models
		Usual Care		
EQ5D	EQ5D	Intervention better than	GEE or	frailty models
		Usual Care		
health care costs	health care costs	Intervention better than	GEE or	frailty models
		Usual Care		
3) Subgroup Analyses:				
To compare the effect of I				
vs UC by different	All primary and	Effects on outcomes	Regres	sion methods with
subgroups: location of	secondary outcomes	differ by location of	approp	riate interaction
practice, patient sex,		practice	term	
age, CHADS2, CHADS-				
VASC, hypertension,				
diabetes and years of				
practice of family doctor				
4) Sensitivity Analyses:	composite of any	Results will remain	i)	patient-level
i) To assess the robustness	AF-related	robust		methods such as
of the results to different	emergency			random-intercept
methods of adjusting for	department visit or			model and
clustering;	unplanned CV			cluster-level [i.e.
ii) To assess the robust	hospitalization			random- and
ness of the results if the				fixed-effects
outcome is treated as the				meta-analytic]
count (number of events)			ii)	GEE using
				Poisson
				distribution

IMPORTANT REMARKS:

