BLEEDING AND STROKE RISK SCORES		'	
CHA ₂ DS ₂	NOT the value REPORTED in PCP chart.		
Score - Mean (SD) Score - n (%)	CALCULATED using documented RFs.		
0			
1			
2			
3 4			
5			
6			
7			
CHA ₂ DS ₂ -VASc	NOT the value REPORTED in PCP chart.		
Score - Mean (SD) Score - n (%)	CALCULATED using documented RFs.		
0			
1			
2			
3			
5			
6			
7			
8			
9 Bleeding risk: HAS-BLED			
Score - Mean (SD)			
Score - n (%)			
1			
2			
3 4			
5			
6			

7		
7 8		
9		
COEXISTING CONDITIONS - n		
(%)		
Previous stroke, systemic	Stroke (Yes) or SE (Yes) or TIA (Yes)	_
embolism or transient	Stroke (163) of 3E (163) of 11A (163)	
ischemic attack		
Congestive heart failure	HF/LV Dysfunction (Yes)	_
Hypertension	Hypertension (Yes) or (Yes-Treated) or (Yes-	
rrypertension	Not Treated)	
Diabetes mellitus	Diabetes (Yes-Not Documented) or (Yes-Type	
Diabetes memeas	1) or (Yes-Type 2)	
Previous myocardial	MI (MM-YYYY) or (ND)	
infarction	(
Vascular disease (any)	Vascular Disease (Yes)	
CAD	CAD (Yes)	
PAD/PVD	Aortic Plaque (Yes)	
UA	PAD/PVD (Yes)	
MI	UA (date) (MM-YYYY) or (ND)	
Aortic plaque	MI (date) (MM-YYYY) or (ND)	
Valvular Heart Disease	Replacement Type (Mechanical) or Mitral	
	Stenosis Type (Moderate) or (Severe)	
Congenial Heart Disease	Congenital Heart Disease (Yes)	
OSA	OSA Dx (Yes)	
Tobacco use		
Former	Tobacco use (Former)	
Current	Tobacco use (Current)	
Alcohol abuse	Alcohol abuse (Yes)	
Pericarditis	Pericarditis (Yes)	
Pulmonary Disease	Pulmonary Disease (Yes)	
INITEDVENITIONS (DDGGEDUDES		
INTERVENTIONS/PROCEDURES		
- n (%)	Vascular Procedure (Vas)	
Vascular procedure (any) CABG	Vascular Procedure (Yes) CABG (Yes)	
PCI	PCI (Yes)	
Ablation (for flutter or AF)	AF Ablation (Yes) or Previous Ablation for Aflu	_
Ablation from matter of All	(Yes)	
Pacemaker / ICD	Pacemaker (Yes)	
Cardioversion		
# of patients	Cardioversion (Yes)	
# of events – median (IQR)	Cardioversions no.	
Bleeding History - n (%)		

Any bleeding	Bleeding History (Yes)	
Intracranial	IC-Intracerebral (Yes) or IC-Other (Yes)	
Non-intracranial	NIC-Epistaxis (Yes) or NIC-GI (Yes) or NIC-	
Non intractation	Other (Yes)	
Major bleeding	Major bleeding (Yes)	
PAST REFERRALS - n (%)	major precumb (res)	
, ,		
AF Clinic	Referred to (AF Clinic)	
Cardiologist	Referred to (Cardiologist)	
Internist	Referred to (Internist)	
Electrophysiologist	Referred to (Electrophysiologist)	
Cath ablation	Referred to (Cath Ablation)	
ED visit for AF within the last		
12 months	ER Visits (Yes)	
# of patients - n (%)	ED Visits	

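### The SAP does not carry over the protocol's bleeding outcomes: major bleeding has no safety designation and no results row of its own, and any bleeding is not listed

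*SAP*

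**What the plan says.** Protocol 2.2 states: "The primary safety outcome is major bleeding". It defines the term by bleeding alone (fatal, critical site, haemoglobin fall or transfusion) and lists any bleeding separately among the secondary clinical outcomes. Systemic embolism appears in that section only as one cause of cardiovascular hospitalization. Protocol 3.7.5 says bleeding will be monitored for safety and that no data safety and monitoring committee is expected.

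The SAP has one primary outcome and eleven secondary outcomes, and no safety outcome. Secondary item 4 is "Systemic embolism / major bleeding". The Secondary Outcomes Analysis section repeats the pairing in its list ("strokes; systemic embolism / major bleeding; mortality; anticoagulant therapy") and sends the list to Table 3. Of Table 1 the SAP says "A summary of all planned analyses is provided in" it; there the pairing occupies a single row, with the hypothesis that the intervention is better and GEE or frailty models as the method. On definitions the SAP says: "The definitions of all outcome variables for the primary and secondary analyses are found in Appendix 1". That appendix is not in the available text.

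**The concern.** The programme is expected to increase the use of proven therapies and improve stroke prevention. Protocol 1.1 itself notes that the benefit of anticoagulation must be balanced against bleeding. Bleeding is therefore the main foreseeable harm if the intervention works as intended. With no monitoring committee expected, the end-of-trial comparison by arm carries most of the safety assessment.

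An analyst who follows the SAP literally has no instruction to analyse any bleeding, nothing marking major bleeding as a safety outcome, and no place in the results table for a bleeding result. The protocol's primary safety question could then be reported only jointly with embolism, or under a grouping chosen after the events are known.

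**Working it through.** No calculation is needed. The check is a comparison of the two documents, item by item.

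| Element | Protocol | SAP |
|---|---|---|
| Safety designation | Major bleeding is the primary safety outcome (2.2) | None |
| Major bleeding as an outcome | Stands alone, with its own definition (2.2) | Only on the line shared with systemic embolism (Secondary Outcomes item 4, Secondary Outcomes Analysis, Table 1) |
| Any bleeding as an outcome | Secondary clinical outcome (2.2) | Not listed; appears only as baseline history in Table 2 |
| Analysis method | GEE for all outcomes (3.9) | GEE for all outcomes (Primary Outcome Analysis); GEE or frailty for the shared line (Table 1) |
| 12-month results row | Not applicable | None in Table 3 |

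**Count of Table 3 outcome rows.** 1 (primary composite) + 6 (AF-related ED visits and five causes) + 6 (unplanned CV hospitalization and five causes) + 3 (stroke and two types) + 1 (all-cause mortality) = 17. Bleeding rows: 0. Systemic embolism appears only inside one cause row under CV hospitalization.

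**Could another row supply the result?**
- The CV hospitalization rows do not. Protocol 2.2 limits that outcome to "Any unplanned hospitalization (admission with an overnight stay in hospital) due to one of the following causes", and bleeding is not among the causes listed.
- The stroke and mortality rows may catch some intracranial or fatal bleeds, but not as bleeding.
- A major bleed that is neither fatal nor intracranial has no row.

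**Is item 4 one outcome or two?** The single Table 1 row for "systemic embolism / major bleeding" points to one. Against that, the SAP never calls the pair a composite, although it uses that word for the primary outcome. Without Appendix 1 the question stays open. The mismatch does not depend on the answer: on either reading the safety label, the any-bleeding outcome and the Table 3 row are absent.

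**Are follow-up data planned?** Protocol 3.7.5 and the events row of Protocol Table 2, which is marked for follow-up, indicate that they are. The bleeding variables in SAP Table 2 describe history at baseline and do not show what is captured at 12 months.

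**The case against.** The strongest reply is that major bleeding remains in the plan. The Secondary Outcomes Analysis section commits to estimating the effect on the shared line, Table 1 gives it a hypothesis and a method, and the remarks after Table 1 say how results will be expressed in all analyses. The SAP does not withdraw Protocol 2.2, and its list of secondary outcomes need not be exhaustive. This stands, and it limits the point: a reader might infer that the primary safety outcome has been abandoned, and the documents do not support that.

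A second reply is that Table 3 is incomplete in general. Only four of the eleven secondary items (1, 2, 3 and 5) have their own row, so the shell does not single out safety. Tables in extracted text can also be damaged. This weakens any inference of intent. It does not supply a bleeding row, and the missing designation and the missing any-bleeding outcome rest on the SAP's running text as well as on Table 3. The other incomplete items are a separate matter.

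A third reply is that the slash may simply separate two outcomes. That is possible. A reader might infer that the SAP merges bleeding and embolism into one endpoint, so that a bleeding difference would be masked. Without Appendix 1 the documents do not establish this, and nothing is claimed here about dilution.

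**Conclusion.** The concern holds as a conflict between the protocol and the SAP in designation, listing and reporting. Of the protocol's two bleeding outcomes, the SAP lists one, on a shared line, and marks neither as a safety outcome; 0 of 17 Table 3 rows report bleeding. A modelled estimate for the shared line is planned, so a method exists. What is not secured is a separate major bleeding result by arm, and any bleeding is not planned for analysis in the SAP.

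Confidence is high for this mismatch only. The conclusion assumes that Table 3 is complete as supplied, and it makes no assumption about what Appendix 1 contains. It says nothing about power: the documents give no bleeding rates, and the trial was sized on the efficacy composite. It should be fixed, and the change is small.

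**What to change.** In the SAP outcome list, Table 1 and Table 3:
- Designate major bleeding, as defined in Protocol 2.2, as the primary safety outcome. Report it alone by arm, with patients, events, effect estimate and 95% CI.
- Add any bleeding as a secondary outcome with its own row.
- Report systemic embolism separately.
- Make the definitions in Appendix 1 match.

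The cost is SAP wording and three table rows (major bleeding, any bleeding, systemic embolism). No new data collection is implied if the follow-up event capture in Protocol 3.7.5 and Protocol Table 2 is carried out as planned; neither passage details how bleeding is recorded, so this should be confirmed. The sample size does not change.
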